### ***Screening procedure***

Our screening procedure is based on the national Breast Cancer Screening Process Technical Guidelines issued in 2015 by the National Health Commission of People's Republic of China as follows:

(1) Clinical examination and initial breast ultrasound screening: all the participants were enrolled and received clinical examination and initial breast ultrasound or AI-assisted ultrasound. The initial screening test results were classified based on BI-RADS; (2) MG re-screening: participants with BI-RADS grade 0 or 3 were then suggested to receive MG. MG results were classified based on BI-RADS; (3) Histopathological examination (hereinafter referred to as biopsy): participants with BI-RADS grade 4 to 5 either in initial ultrasound test or MG test were suggested for further biopsy examination. For patients with MG rescreening of grade 0 or grade 3, short-term follow-up (three to six months) or further biopsy examination were suggested according to experts' evaluation; (4) Follow-up: participants with BI-RADS level 1 to 2 either in ultrasound or MG were under strict follow-up through visits and phone calls by trained medical social workers.

Final screening results (positive or negative) were based on a two-step approach. Initial screening results were determined by breast ultrasound and defined as negative with BI-RADS grade 1 or 2, positive with BI-RADS grade

4 or 5, and indeterminate with BI-RADS grade 0 or 3. Participants with indeterminate initial results were informed of the suspicious lesion detection and referred to MG assessment. The result in this second step was classified as negative or positive according to MG BI-RADS grade.

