Participants receiving final negative results were exempt from additional diagnostic procedures. By contrast, those receiving final positive results were referred to Fudan University Shanghai Cancer Center for further diagnostic work-up to exclude or diagnose breast cancer. To assess interval cancers, we obtained data from all diagnosed breast cancers, plus an additional one year of follow-up from the Shanghai municipal cancer registry, one of the largest cancer registries globally, and an associate member of the International Association of Cancer Registries (IARC). For participants diagnosed with breast cancer outside of screening (ie, diagnosed with interval cancer), we collected all medical records. Two experienced radiologists reviewed the screening MG and ultrasound images from the study and the clinical MG and ultrasound images used for diagnosis of breast cancer, and reached a consensus on whether or not the breast cancer could retrospectively be identified in the screening.

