### ***Outcomes***

The primary endpoint of this study was to assess, and compare, the difference in the incidence of early breast cancer between two groups using different breast cancer screening methods (AI-assisted ultrasound screening/routine ultrasound screening). Early cancers should meet any of the following criteria at the time of diagnosis: less than 20 millimeters in diameter, no metastatic lymph nodes in the axilla, no distant metastasis, non-invasive cancers, stage 0, stage I, and stage IIA IIB (T2N1M0) breast cancer according to AJCC 8th staging.

The secondary aim was to determine the sensitivity, specificity, positive predictive value, and negative predictive value of the screening methods (AI-assisted ultrasound screening/routine ultrasound screening). Screening-detected cancers were defined as breast cancers positive for screening tests. We defined interval cancers as: breast cancers diagnosed after a negative screening test; breast cancers diagnosed after an indeterminate screening

test, but without any follow-up mammography or diagnostic examinations. A true-positive screening result was a positive result in a participant who was diagnosed with breast cancer by further diagnostic work-up. A false-positive screening result was a positive result in the absence of breast cancer. A true-negative screening result was a negative result in the absence of breast cancer and a false-negative test result was a negative result followed by diagnosis of interval cancer.

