#### ***Statistical analysis***

Numerical data were shown as means and standard deviation (SD) and categorical variables in percentages. Sensitivity was determined via dividing the numbers of true-positive screening by the numbers of true-positive and false-positive screening. Specificity was determined via dividing the numbers of true-negative screening by the numbers of true-negative and false-negative screening. To calculate 95% CIs, we did bootstrapping based on 5000 samples. The significance of the differences of incidences was assessed using Poisson regression. For categorical variables we used Fisher's exact test or likelihood-based  $\chi^2$  test.

All analyses were done with IBM SPSS (version 20).

This study was performed according to the guidelines of the Helsinki Declaration and was approved by the Medical Ethics Committee of Fudan University Shanghai Cancer Center (No. 2008223-22). Informed consent was obtained from all individual participants included in the study.

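### Sensitivity and specificity are printed with the predictive-value formulas, and the false-negative rule, read literally, leaves out one of the plan's two types of interval cancer

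*Combined protocol and SAP*

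**What the plan says.** The secondary aim in Outcomes names four measures for each screening method: sensitivity, specificity, positive predictive value (PPV) and negative predictive value (NPV).

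Statistical analysis gives formulas for two of them. For the first it says: "Sensitivity was determined via dividing the numbers of true-positive screening by the numbers of true-positive and false-positive screening". The denominator is therefore every woman who tests positive. For the second, the denominator is every woman who tests negative: "Specificity was determined via dividing the numbers of true-negative screening by the numbers of true-negative and false-negative screening".

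Outcomes defines two types of interval cancer. The first follows a negative test. The second follows an indeterminate test, "but without any follow-up mammography or diagnostic examinations". The false-negative rule comes a few sentences later: "a false-negative test result was a negative result followed by diagnosis of interval cancer".

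Screening procedure sets out how a result becomes final: "Final screening results (positive or negative) were based on a two-step approach". An initial ultrasound is negative at BI-RADS 1 or 2, positive at 4 or 5, and "indeterminate with BI-RADS grade 0 or 3". The second step is mammography: "participants with BI-RADS grade 0 or 3 were then suggested to receive MG". The mammography grade then decides between negative and positive. The same section describes interval cancers more broadly: "For participants diagnosed with breast cancer outside of screening (ie, diagnosed with interval cancer), we collected all medical records".

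**The concern.** There are two defects, of unequal weight.

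The formulas are the larger one. TP/(TP+FP) is PPV, and TN/(TN+FN) is NPV. Sensitivity should be conditional on having cancer and specificity on being free of it; the printed forms condition on the test result instead. An analyst who follows the text would report PPV under the name of sensitivity and NPV under the name of specificity, so two of the four planned measures would not be estimated.

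The false-negative rule is the lesser one. It requires a negative result. A woman with an indeterminate ultrasound who has no mammography never receives a negative or positive result under the stated steps. If she is later diagnosed with cancer, the plan calls it an interval cancer but, taken literally, gives it no cell. A cancer-free woman with the same history has no cell either. If the formula is corrected and this rule is left alone, sensitivity will be too high whenever such a cancer occurs. Only the secondary accuracy measures are at stake.

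**Working it through.** **Scale.** Sample size calculation gives 16,000 women and an incidence of 125.75/100,000: 16,000 × 125.75/100,000 = 20.12 cancers (the plan states 20). With 83% at early stage, 20.12 × 0.83 = 16.7 (the plan states about 17). The plan's figures reproduce. The section does not say whether 16,000 is a total or a number per arm; it is taken as a total here.

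**Effect of the printed formulas.** Assumptions: the section's 5/1000 is the screen-positive rate, so 16,000 × 5/1000 = 80 positives; there are 20 cancers, of which 16 are detected. Then TP = 16, FP = 80 − 16 = 64, FN = 4 and TN = 16,000 − 80 − 4 = 15,916.

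| Measure | As printed | Standard form |
|---|---|---|
| Sensitivity | TP/(TP+FP) = 16/80 = 20.0% | TP/(TP+FN) = 16/20 = 80.0% |
| Specificity | TN/(TN+FN) = 15,916/15,920 = 99.975% | TN/(TN+FP) = 15,916/15,980 = 99.599% |

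**Where a second-type interval cancer falls.** A true positive needs a positive result, and a false negative needs a negative one. An indeterminate ultrasound becomes either only through a mammography grade, and this woman has none. No default is stated, so the literal reading leaves the cancer unclassified.

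**Effect on corrected sensitivity.** Let k be the number of second-type cancers left out. The upward shift is TP/(TP+FN) − TP/(TP+FN+k). It is zero for k = 0 and positive for any k ≥ 1 with TP > 0. The documents do not give k.

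| Assumed cancers in all, k = 1 | TP | Left out | Counted | Shift (points) |
|---|---|---|---|---|
| 20 | 12 | 12/19 = 63.2% | 12/20 = 60.0% | 3.2 |
| 20 | 16 | 16/19 = 84.2% | 16/20 = 80.0% | 4.2 |
| 20 | 19 | 19/19 = 100% | 19/20 = 95.0% | 5.0 |
| 10 (one arm) | 5 | 5/9 = 55.6% | 5/10 = 50.0% | 5.6 |
| 10 (one arm) | 9 | 9/9 = 100% | 9/10 = 90.0% | 10.0 |

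The rows with 10 cancers assume an equal split of 20 between the arms. They matter because Outcomes asks for the accuracy of each method. For comparison with sampling error, the exact (Clopper-Pearson) 95% intervals are 60.4 to 96.6% for 16/19 and 56.3 to 94.3% for 16/20.

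**Effect on NPV and specificity (standard forms).** Take 16 TP, 64 FP, 3 FN and k = 1, and assume that 160, 800 or 1,600 women (1%, 5% or 10%) are indeterminate without follow-up and left out. TN is then 16,000 − 80 − 3 minus that number: 15,757, 15,117 or 14,317.
- NPV is 99.981, 99.980 or 99.979%, against 99.975% with all of them classified as not positive. The difference is under 0.01 point.
- Specificity is 99.595, 99.578 or 99.555%, against 99.599%. The difference is under 0.05 point.

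**The case against.** On the formulas, the best defence is that they are slips of wording and that the analysis would use the usual definitions. That may be so, but the printed text is the only specification, and it is wrong for both measures.

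On false negatives the defence is stronger. Outcomes defines interval cancer to include both types and then uses that term in the false-negative rule. Screening procedure equates interval cancer with any cancer diagnosed outside screening and says that final results are positive or negative. Women with an indeterminate ultrasound were not only advised to have mammography but also described as referred for it. Together these make it natural to read every interval cancer as a false negative. This stands as evidence of intent. It does not settle the matter: the rule still requires a negative result, and no sentence assigns one to a woman who skips the second step. That Outcomes has a second type at all shows that such women were foreseen.

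Three further points stand. As printed, sensitivity contains no false-negative term, so the gap cannot affect it until the formula is corrected. The effect needs at least one such cancer. And in the pooled illustration, a shift of one cancer is well within sampling error.

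It is also fair to say that nothing in the documents requires unresolved cancer-free women to be called true negatives. Their ultrasound had shown something suspicious, and scoring them as not positive charges the ultrasound method with non-attendance at mammography. A separate inconclusive category is equally defensible.

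**Conclusion.** The concern holds. The formula error is unconditional and plain on the page. Its illustrated size, 20.0% instead of 80.0% for sensitivity, rests on the assumed counts.

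The false-negative gap is an ambiguity whose literal reading conflicts with the plan's own definition of interval cancer. Given a corrected sensitivity and the literal reading, the direction is certain: each omitted cancer raises sensitivity. One omitted cancer does so by about 3 to 5 points with 20 cancers in total (TP 12 to 19), or about 6 to 10 points with an assumed 10 in an arm (TP 5 to 9). NPV and specificity barely move. The primary endpoint, early-cancer incidence, is unaffected.

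A reader might infer that the plan knowingly excludes these cancers, so that reported sensitivity must be inflated, or that the comparison of arms is biased. The documents support neither. They suggest that both types were meant to count. They give no number of second-type cancers, which may be zero, and no indeterminate rate or mammography uptake for either arm.

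**What to change.** In Statistical analysis, print sensitivity as TP/(TP+FN) and specificity as TN/(TN+FP), and give TP/(TP+FP) and TN/(TN+FN) under their proper names, PPV and NPV.

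In Outcomes, define a false negative as either type of interval cancer.

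Report by arm the number of women with an indeterminate ultrasound and the number of those without follow-up.

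For the accuracy analysis only, state one rule for unresolved women without cancer, and repeat specificity and NPV with the alternative. For example, count them as true negatives in one analysis and keep them as a separate inconclusive category in the other.

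The cost is a few lines of text and recoding of existing records, with no new data. Compared with a corrected sensitivity that omits these cancers, the new false-negative definition can only lower the estimate or leave it unchanged.

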#### ***Sample size calculation***

Sample size was primarily calculated by expected detection and incidence data from breast cancer. According to the positive detection rate of Asian women with suspicious breast cancer lesion (5/1000), 16,000 participants were required. Based on the reported data by Shanghai Center for Disease Control and Prevention in 2017, the age-specific incidence rate of breast cancer among women aged 35-69 in urban Shanghai was 125.75/100,000, so that 20 breast cancer cases were expected to be screened. Our previous breast cancer screening study showed that the early stage rate of screen-detected breast cancer reached 83%, predicting about 17 breast cancer at early stage would be diagnosed in this study. All this would meet the evaluation needs of endpoint indicators.

#### ***Statistical analysis***

Numerical data were shown as means and standard deviation (SD) and categorical variables in percentages. Sensitivity was determined via dividing the numbers of true-positive screening by the numbers of true-positive and false-positive screening. Specificity was determined via dividing the numbers of true-negative screening by the numbers of true-negative and false-negative screening. To calculate 95% CIs, we did bootstrapping based on 5000 samples. The significance of the differences of incidences was assessed using Poisson regression. For categorical variables we used Fisher's exact test or likelihood-based  $\chi^2$  test.

All analyses were done with IBM SPSS (version 20).

This study was performed according to the guidelines of the Helsinki Declaration and was approved by the Medical Ethics Committee of Fudan University Shanghai Cancer Center (No. 2008223-22). Informed consent was obtained from all individual participants included in the study.

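### The formulas written for sensitivity and specificity are those of the positive and negative predictive values

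*Combined protocol and SAP*

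**What the plan says.** The Outcomes section sets the secondary objective: "The secondary aim was to determine the sensitivity, specificity, positive predictive value, and negative predictive value of the screening methods", for AI-assisted and routine ultrasound. It defines the four cells in the usual way. For example, "A true-positive screening result was a positive result in a participant who was diagnosed with breast cancer by further diagnostic work-up", and "a false-negative test result was a negative result followed by diagnosis of interval cancer". A false positive is a positive screen without cancer; a true negative is a negative screen without cancer.

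The Statistical analysis section then gives two formulas:

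- The first takes all screen-positive women as its denominator: "Sensitivity was determined via dividing the numbers of true-positive screening by the numbers of true-positive and false-positive screening"
- The second takes all screen-negative women as its denominator: "Specificity was determined via dividing the numbers of true-negative screening by the numbers of true-negative and false-negative screening"

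It gives no formula for PPV or NPV. Confidence intervals for these measures come from 5,000 bootstrap samples.

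The Outcomes section also has a two-part definition of interval cancer. The first part is cancer after a negative screen. The second is cancer after an indeterminate "test, but without any follow-up mammography or diagnostic examinations". The Screening procedure section treats indeterminate (BI-RADS 0 or 3 on the initial ultrasound) as a category separate from negative.

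**The concern.** Sensitivity is the share of women with cancer whom the screen finds, so its denominator must be the women with cancer. Specificity is the share of women without cancer whom the screen clears, so its denominator must be the women without cancer. Both written formulas divide by the screening result instead.

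The consequences differ for the two measures. The written sensitivity ignores missed cancers and falls as false positives rise, so false-positive counts alone can hide, create or reverse a difference between the arms. The written specificity ignores false positives and responds only to the few missed cancers, so it stays near 100% however many women are recalled needlessly.

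The plan also goes to some trouble to find missed cancers: "To assess interval cancers, we obtained data from all diagnosed breast cancers, plus an additional one year of follow-up" from the municipal cancer registry. Under the written formula none of that information reaches sensitivity.

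A second point affects the repair. A false negative is defined as a negative result followed by interval cancer. Read literally, a cancer after an indeterminate result without follow-up is an interval cancer but not a false negative, and it is not a true positive either. It would drop out of even the correct sensitivity.

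**Working it through.** **Identity.** With TP, FP, TN and FN as defined in the Outcomes section:

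| Measure | Standard formula | As written |
|---|---|---|
| Sensitivity | TP/(TP+FN) | TP/(TP+FP), which is PPV |
| Specificity | TN/(TN+FP) | TN/(TN+FN), which is NPV |

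This needs no numbers. The rest shows the size.

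**The plan's own figures.** The plan states no expected sensitivity or specificity. Its case numbers in the Sample size calculation section do reproduce: 16,000 × 125.75/100,000 = 20.12, stated as 20; 20.12 × 0.83 = 16.7, stated as about 17. They are used here only for scale.

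**Assumptions.** 8,000 women per arm (half of 16,000; the plan gives no allocation). The 5/1000 detection rate is read as final screen-positives: 8,000 × 5/1000 = 40. Cancers per arm, found or missed: 8,000 × 125.75/100,000 = 10.06, taken as 10. The split into detected and missed is assumed.

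| | 1 missed | 3 missed |
|---|---|---|
| TP, FN, FP, TN | 9, 1, 31, 7,959 | 7, 3, 33, 7,957 |
| Sensitivity, standard | 9/10 = 90% | 7/10 = 70% |
| Sensitivity, as written | 9/40 = 22.5% | 7/40 = 17.5% |
| Specificity, standard | 7,959/7,990 = 99.61% | 7,957/7,990 = 99.59% |
| Specificity, as written | 7,959/7,960 = 99.99% | 7,957/7,960 = 99.96% |

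**Whole trial, other reading of the 20 cases.** Suppose the 20 are all screen-detected among 16,000 × 5/1000 = 80 positives. As missed cancers go from 0 to 10, standard sensitivity falls from 20/20 = 100% to 20/30 = 66.7%. The written value is 20/80 = 25% throughout.

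**Reversal between arms.** Let arm B be the second column (7/40 = 17.5% as written). Arm A has TP = 9 and FN = 1. It scores below B as written once its false positives exceed 9 × 33/7 = 42.4. At 43, A scores 9/52 = 17.3%, although its true sensitivity is 90% against 70% in B. Twelve more screen-positives in A (52 against 40) are enough.

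**Specificity with more false positives.** Keep TP = 9 and FN = 1, and let FP = 400, so TN = 7,590. Standard specificity is 7,590/7,990 = 94.99%; the written value is 7,590/7,591 = 99.99%, as it was with 31 false positives.

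**Unclassified cancers.** Take TP = 7, FN = 1 and 2 cancers after an indeterminate result without follow-up. The correct formula gives 7/8 = 87.5% if the two are dropped and 7/(7+1+2) = 70% if they count as missed.

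**The case against.** The best defence is that this is a drafting slip with no effect on the results. The cells are defined conventionally, the four measures are listed separately, and interval cancers are collected, all of which suggests that the authors know what sensitivity is. That may be so. But the same swap occurs in both sentences, the text reports it as what was done, and no other specification exists. The defence is a reason to check the code, not to leave the formulas.

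On the indeterminate cancers, one can argue that false negatives were meant to cover every interval cancer, since otherwise the second part of that definition does nothing for the accuracy measures. That reading is possible, but the wording does not support it, so the plan should state its rule. It is also fair to say that this rule alone does not complete the table: the Screening procedure section calls the mammography step positive or negative without saying where mammography grades 0 and 3 fall.

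The illustrations can be challenged as well. Arm sizes, the meaning of the 5/1000 rate and the missed cancers are assumed; 400 false positives is about 13 times the 31 in the base table; and the reversal is narrow (17.3% against 17.5%). It shows that reversal is possible, not that it is likely. The identity does not depend on any of these choices.

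**Conclusion.** The point holds and must be fixed. As written, sensitivity is PPV and specificity is NPV, so two of the four secondary accuracy measures and their bootstrap intervals would be wrong if the text was followed. On the assumptions above (40 positives and 10 cancers per 8,000 women, 1 to 3 missed), a sensitivity of 90% to 70% would be reported as 22.5% to 17.5%. The error in specificity is under half a percentage point at that positive rate, but about 5 points with 400 false positives per arm.

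Two limits apply. The primary endpoint, early-cancer incidence compared by Poisson regression, does not use these formulas. And the document does not show which formulas the analysis used. The handling of cancers after an indeterminate result is a lesser gap in the same definitions, but it can move a correctly calculated sensitivity materially when there are so few cancers.

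**What to change.** Replace the two sentences in the Statistical analysis section with four formulas:

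- sensitivity = TP/(TP+FN)
- specificity = TN/(TN+FP)
- PPV = TP/(TP+FP)
- NPV = TN/(TN+FN)

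Add a rule to the Outcomes section on how interval cancers after an indeterminate result without follow-up are classified, and report sensitivity with and without them. The same rule can state which cell women with mammography grade 0 or 3 enter.

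Check the analysis code against these definitions. Recompute any estimate, interval or comparison between arms that used the written formulas.

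The cost is a few sentences, a code check and, if needed, a rerun of simple proportions with their bootstrap intervals. No new data are required.

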### ***Randomization method***

Randomization was conducted by cluster, where districts rather than individuals were chosen as units of randomization. In order to avoid transfer between control and intervention cluster, urban levels were used as our strata. We then randomly selected one district out of seven urban areas as intervention cluster and another one out of nine suburban areas as control cluster.

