### ***Participants and intervention***

Two women and children's care centers from randomly selected two districts were the main study locations. Women in the intervention arm received AI-assisted ultrasound conducted by trained female primary health workers, while women in the control arm received routine ultrasound conducted by doctors from the Maternal and Child Health Hospital. Participants in both arms were eligible for further diagnostic evaluation and treatment at Fudan university Shanghai cancer center and women in both groups were offered access to obtain rapid treatment at the hospital. Recruitment was started in January 2021 and completed in December 2022. All participants were then followed up till the end of 2023. The database was sealed in January 2024 for analysis.

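### The analysis plan names no clustering unit, so intervals for specificity and positive-call rates will be too narrow if ultrasound operators differ in their thresholds

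*Combined protocol and SAP*

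**What the plan says.** The Statistical analysis section gives the whole inferential plan in three statements. For intervals: "To calculate 95% CIs, we did bootstrapping based on 5000 samples". For the primary comparison: "The significance of the differences of incidences was assessed using Poisson regression". For the rest: "For categorical variables we used Fisher's exact test or likelihood-based" chi-square tests. No cluster unit, random effect, robust variance, intraclass correlation (ICC) or design effect appears, and the Sample size calculation makes no allowance for clustering.

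Participants and intervention describes who did the scanning. "Women in the intervention arm received AI-assisted ultrasound conducted by trained female primary health workers". In the other arm, hospital doctors performed the unassisted scans. How many operators there were, and how many women each scanned, is not stated.

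Under Screening procedure, the ultrasound BI-RADS grade makes the initial result negative, positive or indeterminate. Indeterminate results (grades 0 and 3) go to mammography, which then decides. Outcomes lists sensitivity, specificity, PPV and NPV as the secondary aim. Under Randomization method, "districts rather than individuals were chosen as units of randomization", with one district per arm.

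**The concern.** A BI-RADS call depends partly on the person making it. If some operators call more lesions suspicious than others do, false positives cluster by operator. An analysis that counts each woman as an independent unit then leaves out the between-operator variance. The specificity interval comes out too narrow, and a few high-calling operators in one arm could produce a nominally significant difference between two methods that perform equally.

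Fisher's exact and chi-square tests assume independent women, and so does Poisson regression as written. The bootstrap does too on its ordinary reading, since no other unit is named. This problem is separate from having one district per arm. Between-district variance cannot be estimated from two districts, but operator variance can be estimated within each arm from the trial's own data.

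**Working it through.** **The plan's own figures (Sample size calculation).** 16,000 × 125.75/100,000 = 20.1 cancers (stated: 20). 20.1 × 0.83 = 16.7 early cancers (stated: about 17). Both reproduce.

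**False-positive rate.** 16,000 × 5/1000 = 80 positives. Reading these as final positives and counting all 20 cancers among them leaves 80 − 20 = 60 false positives in 16,000 − 20 = 15,980 women without cancer. So p = 60/15,980 = 0.375%.

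**Assumptions not in the documents.** 8,000 women per arm; k operators per arm with equal caseloads m = 8,000/k; between-operator coefficient of variation (CV) of the false-positive rate from 0.3 to 0.8, the same in both arms.

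**Formulas.** ICC = CV² × p/(1 − p). Design effect = 1 + (m − 1) × ICC. Ratio of true to naive standard error = √(design effect).

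Central case, k = 10 and CV = 0.5: ICC = 0.25 × 60/15,920 = 0.00094; design effect = 1 + 799 × 0.00094 = 1.75; ratio = √1.75 = 1.32.

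| Operators per arm | Women each | CV | Design effect | SE ratio | Coverage of naive 95% CI | Size of naive 5% z test |
|---|---|---|---|---|---|---|
| 40 | 200 | 0.3 | 1.07 | 1.03 | 92% | 6% |
| 10 | 800 | 0.5 | 1.75 | 1.32 | 84% | 14% |
| 5 | 1,600 | 0.8 | 4.86 | 2.20 | 60% | 37% |

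Coverage and test size come from 20,000 simulated trials per setting with gamma-distributed operator rates. With no operator variation, the simulation gives 93% coverage and 5% test size. About two points of the coverage shortfall therefore come from the rare event and not from clustering. Fisher's test is more conservative: about 11% in the central case, and no more than the nominal 5% in the mildest.

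**Absolute scale.** The naive 95% half-width is 1.96 × √(0.00375 × 0.99625/8,000) = 0.13 percentage points. Multiplied by 1.32 and 2.20, it becomes 0.18 and 0.30 points.

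**A second model.** A beta-binomial simulation used 20 operators of 400 women per arm and a 0.5% rate. At ICC 0.001, 0.005 and 0.01, a woman-level bootstrap covered 92%, 76% and 63%, and an operator-level bootstrap 94%, 92% and 88%. The unadjusted chi-square test rejected in 10%, 25% and 36% of null trials. The two larger ICCs imply CVs of about 1.0 and 1.4, outside the range in the table.

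**Other measures, central case.**
- PPV: with about 10 true and 30 false positives per arm, the naive variance of the log odds is 1/10 + 1/30 = 0.133. Operator variation adds CV²/k = 0.25/10 = 0.025. The ratio is √(0.158/0.133) = 1.09; the checks made put the effect at about 7–10%. It is 1% with 40 operators and CV 0.3, and 40–50% only with 5 operators and CV 0.8.
- Early-cancer incidence: 16.7/2 = 8.35 events per arm, or 0.84 per operator. Overdispersion is 1 + 0.84 × 0.25 = 1.21, so the interval is 10% wider (5% with 20 operators).
- Sensitivity: about one cancer per operator, so almost no effect.

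**Candidate remedies.** In the central case, operator-clustered standard errors with a t reference bring coverage to about 94% and test size to 5%. Resampling whole operators gives a standard error about 0.95 of the true one. Resampling operators and then women within them counts within-operator variance twice: its standard error was about 1.2 to 1.4 times the true one in the settings tried, including one with no operator effect.

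**The case against.** The strongest reply is that the size of the problem rests on three quantities the documents do not give: the number of operators, their caseloads and how much they differ. Over the assumed range the effect runs from trivial to severe. That stands, so only the direction is established and the sizes are conditional.

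Four further points stand in whole or part.
- For grades 0 and 3, mammography sets the final result. An unknown share of final positives is therefore not the ultrasound operator's call, and the figures above are upper figures to that extent.
- The bootstrap's unit is unstated. That it resamples single women is the ordinary reading, not a documented fact.
- The formula printed for specificity, TN/(TN + FN), is that of NPV. Until it is corrected, the interval labelled specificity describes a different quantity, to which the figures above do not apply.
- Outcomes speaks of determining accuracy and reserves comparison for the primary endpoint. This weakens the concern about between-arm tests, but not about each arm's own interval.

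It can also be said that one district per arm makes operator clustering beside the point. For between-arm P values that is largely right. It is no reason to leave out a variance component that can be estimated from each arm's own specificity interval.

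A reader might infer that every interval and test in the plan is materially wrong, or that each operator is known to have scanned hundreds of women. The documents support neither. Caseloads are not given, and PPV, sensitivity and the primary comparison have too few events per operator for much effect in the central case.

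**Conclusion.** The point holds for true specificity and positive-call rates. The plan states no allowance for correlation among women graded by the same operator, and any real variation in operator threshold makes woman-level intervals for these measures too narrow. Under the stated assumptions the understatement runs from negligible (3%) to more than twofold, with a central value of about a third. In absolute terms the central change is from ±0.13 to ±0.18 percentage points, which matters mainly if the arms are compared.

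It does not extend with any force to PPV (about 7–10% in the central case), sensitivity or the primary incidence comparison. Nor should a reader infer that operator-level analysis would make between-arm P values valid tests of AI assistance: operators are nested in one urban and one suburban district, and method cannot be separated from district. The change is worth making, but the primary result does not turn on it.

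**What to change.** In Statistical analysis:

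1. State the bootstrap's resampling unit. For specificity and positive-call rates, resample whole operators within arm, keep all their women, and do not resample women a second time. Alternatively, use GEE or regression with operator-clustered standard errors and a small-sample (t) correction.
2. Compute specificity as TN/(TN + FP).
3. Report the number of operators and the caseload of each, by arm.
4. State that intervals are conditional on the two districts and that between-arm P values are descriptive.

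The cost is SAP wording and one extra variable, the operator ID, which is assumed to be on the examination record. The downside is wider, less favourable intervals. With very few operators, even the operator-level interval may fall somewhat short of nominal coverage.
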